17.6.3. ABNORMAL INVOLUNTARY MOVEMENT SCALE (AIMS)

The AIMS is a clinician-rated assessment of abnormal movements consisting of unobtrusive observation of the subject at rest (with shoes removed) and several questions or instructions directed toward the subject. It contains seven items related to: facial, lip, jaw, and tongue movements, upper and lower extremity movements, and trunk movements. Three other items assess the subject at a global level, and two items assess dental status. The individual items on the AIMS are rated from 0 = ‘None’ to 4 = ‘Severe’. The (non-global) total AIMS score is the sum of items 1 through 7. The possible range for the total AIMS score is 0 to 28. Items 8 through 12 are not included in the total AIMS score. Higher values of the total AIMS score indicate increased severity in abnormal movement. If 1 or more of the AIMS total score items are missing at a visit, the score will be set to missing. Item 8, representing global severity score, will be summarized separately. AIMS is assessed at Visit 2/Baseline/Week 0, Visit 3/Week 1, Visit 4/Week 2, Visit 5/Week 4, and Visit 6/Week 6.

Document:

Author:

Version Number:

V2.0

Version Date:

21MAY2020

Template No: CS_TP_BS016 Revision 4
Effective Date: 01Apr2016

Reference: CS_WI_BS005

All summaries and analyses will be based on the SAF population. Descriptive statistics for absolute value and change from baseline will be displayed at each visit by treatment group. Each total score will be analyzed using MMRM and ANCOVA based on the change from baseline to Week 6 similar to the primary efficacy endpoint, with the respective baseline values as covariate (see [Sections 16.1.3](#) and [16.1.5.1](#)).

The AIMS total score at each visit will also be classified as 'abnormal' if either: at least two items have a response of 'mild' or higher; or at least one item has a response of 'moderate' or higher. Otherwise, non-missing total scores will be classified as 'normal'. This is a modification of the Schooler-Kane Criteria for Tardive Dyskinesia ([Schooler 1982](#)). Shifts from baseline will be summarized by visit, postbaseline overall (based on maximum severity), and treatment group.

Frequency distribution of AIMS global severity score will be provided by visit and treatment group. Postbaseline AIMS global severity scores will be classified as 'worsened', 'unchanged', or 'improved', relative to a subject's baseline score. A higher score than that of baseline would be classified as 'worsened'. Conversely, a lower score would be classified as 'improved'. These postbaseline changes will be summarized by visit and treatment group.

17.6.4. BARNES AKATHISIA RATING SCALE (BARS)

The BARS is a rating scale geared toward assessment of neuroleptic-induced akathisia, though it can be used to measure akathisia associated with other drugs as well. The BARS consists of four items, including one item assessing objective restlessness, two items targeting subjective restlessness (awareness and related distress), and one global clinical assessment item. All items are anchored and utilize a 4-point scale, except for the global rating which has a 6-point scale (from absence of akathisia through severe akathisia). The subjective and objective items are summed to yield a total score. The BARS total score is the sum of items 1 through 3 and ranges from 0 to 9. Higher values of the BARS total score indicate higher severity of akathisia. If one or more of items 1 to 3 at a visit are missing the total will not be calculated. BARS is assessed at Visit 2/Baseline, Visit 3/Week 1, Visit 4/Week 2, Visit 5/Week 4, and Visit 6/Week 6.

All summaries and analyses will be based on the SAF population. Descriptive statistics for absolute value and change from baseline in BARS total score and global clinical assessment score will be displayed at each visit by treatment group. The BARS total score and global clinical assessment score will be analyzed using MMRM and ANCOVA based on the change from baseline to Week 6 similar to the primary efficacy endpoint, with the respective baseline values as covariate (see [Sections 16.1.3](#) and [16.1.5.1](#)).

Categorical scores for the four BARS items will be summarized with number and percentage of observations by visit and treatment group.

The postbaseline BARS Global Clinical Assessment of Akathisia responses will be classified as 'worsened', 'unchanged', or 'improved', relative to a subject's baseline response. A higher score than that of baseline would be classified as 'worsened'. Conversely, a lower score would be classified as 'improved'. Shifts from baseline will be summarized by visit and treatment group.

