10.3.3. Concomitant Psychotropic/Antipsychotic Medications

Treatment with benztropine (up to 6 mg/day) will be permitted as needed for movement disorders. In cases where benztropine is not available or a subject has had an inadequate response or intolerance to benztropine treatment, the following medications may be used to treat acute EPS: biperiden (up to 16 mg/day) or trihexyphenidyl (up to 15 mg/day) or diphenhydramine (up to 100 mg/day). Treatment with propranolol (up to 120 mg/day) or amantadine (up to 300 mg/day) will be permitted as needed for akathisia. These allowed medications for the treatment of EPS, akathisia, and dystonia may be given in any formulation (oral, IM, or IV) as deemed appropriate by the investigator. Medications used to treat movement disorders should not be given prophylactically. Medications used for movement disorders should be tapered and discontinued prior to randomization but may be reinstated if symptoms emerge.

In situations where anticholinergic agents or sedative/hypnotic agents (or any agents that may cause sedation) are administered, these should be taken at the same time each day and should not be taken within 8 hours of scheduled assessments. In regions that do not have the specified drugs available, similar drugs at equivalent dosages will be substituted as described in the Study Reference Manual or in consultation with the Medical Monitor.

Concomitant use of sedative hypnotics is permitted during Screening and for Weeks 1-3 (through Visit 5) at the discretion of the Investigator with the following restrictions: Lorazepam is permitted at the discretion of the Investigator up to 2 mg/day for intolerable anxiety/agitation, as clinically indicated. Lorazepam should be used sparingly, when clinically required, per investigator judgment. Lorazepam (≤ 2 mg/day), eszopiclone (≤ 3 mg/day), zopiclone (≤ 7.5 mg/day), zolpidem (≤ 10 mg/day), zolpidem CR (≤ 12.5 mg/day) and temazepam (≤ 30 mg/day) may be administered at bedtime for insomnia, as needed. Hypnotic agents should be administered no more than once nightly and should not be used in combination. Continued use of the above sedative hypnotics beyond Visit 5 requires approval from the Medical Monitor.

Anxiolytics, sedatives or hypnotics should not be administered within 8 hours prior to any psychiatric assessments.

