6.3. DERIVED TIME POINTS

As per protocol, Visit 6 can be an End of Treatment (EOT) visit or an Early Termination (ET) visit. If a subject terminates early, his/her ET visit will be mapped to the next planned assessment visit if it is within the window of the next planned assessment visit. This applies to both efficacy and safety data. If assessments from an ET visit cannot be mapped to the next planned assessment visit, these assessments will be excluded from any mixed model for repeated measures (MMRM) or analysis of covariance (ANCOVA) analysis. No follow-up visit data will be included in any MMRM/ANCOVA analyses. In the case of the ET being out of window of the next planned visit, it will be mapped to an unscheduled visit as appropriate.

All applicable by-visit efficacy and safety tables will include descriptive statistics for the Follow-up visit and the "Last observation visit". The "Last observation visit" is defined as the post-baseline visit at which the last non-missing observation is collected for a subject for a given parameter, including unscheduled visits or unmapped ET visits. The "Last observation visit" will be excluded from any MMRM/ANCOVA analyses.

For remapping of the ET visits, see Table 1 below.

Table 1: Mapping of the ET visit.

Parameter	Early Termination Day Criteria	Week	Analysis Visit
ECG, Vital Sign, YMRS, C-SSRS, Concomitant Medication, Last dose of Benzodiazepines/ Sedatives/Hypnotics	1 ≤ study day ≤ 9	1	Visit 3/Week 1
	10 ≤ study day ≤ 16	2	Visit 4/ Week 2
	17 ≤ study day ≤ 30	4	Visit 5/Week 4
	31 ≤ study day ≤ 44	6	Visit 6/Week 6
MADRS, CGI-BP-S, HAM-A, QIDS-SR16, AIMS, BARS, SAS	1 ≤ study day ≤ 9	1	Visit 3/Week 1
	10 ≤ study day ≤ 16	2	Visit 4/Week 2
	17 ≤ study day ≤ 30	4	Visit 5/Week 4
	31 ≤ study day ≤ 44	6	Visit 6/Week 6
SDS, EQ-5D-5L, Weight, BMI, Waist Circumference, PWC, HbA1C, Lipid panel, Serum Insulin, HOMA-IR, CRP	1 ≤ study day ≤ 44	6	Visit 6/Week 6

Document:

Author:

Version Number:

V2.0

Version Date:

21MAY2020

Template No: CS_TP_BS016 Revision 4
 Effective Date: 01Apr2016

Reference: CS_WI_BS005

Hematology, Serum Chemistry*, Urinalysis, Serum Prolactin, PK, Plasma Prolactin	1 ≤ study day ≤ 16	2	Visit 4/Week 2
	17 ≤ study day ≤ 44	6	Visit 6/Week 6

* Except for parameters listed above such as HbA1C, Lipid panel, Serum Insulin, HOMA-IR, CRP.

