6.4. RETESTS, UNSCHEDULED VISITS AND EARLY TERMINATION DATA

In general, for by-visit summaries, data recorded at the scheduled visits will be presented.

Unscheduled measurements will not be included in by-visit summaries. Unscheduled measurements collected prior to the first dose of study drug will contribute to the derivation of the baseline value. Unscheduled measurements collected postbaseline will contribute to the derivation of markedly abnormal postbaseline value, and best/worst case value where required (eg, shift tables).

Early termination data collected postbaseline will be assigned to the next planned visit for that assessment as explained in [Section 6.3](#). This mapping will be implemented to all early termination data points used in the efficacy and safety analyses.

Listings will include scheduled, unscheduled (including retests), and early termination data with original dates and visits displayed.

Document:

Author:

Version Number:

V2.0

Version Date:

21MAY2020

Template No: CS_TP_BS016 Revision 4
 Effective Date: 01Apr2016

Reference: CS_WI_BS005

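### BARS and SAS shifts are tabulated by visit only, so subjects who ever worsened on these scales are not counted; the loss is confined to EPS that resolves or is treated on study.

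*SAP*

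**What the plan says.** SAP 17.6.4 classes each post-baseline BARS global assessment as worsened, unchanged or improved relative to baseline, and then states: "Shifts from baseline will be summarized by visit and treatment group". The BARS items are handled likewise: "Categorical scores for the four BARS items will be summarized with number and percentage of observations by visit and treatment group". SAP 17.6.5 classes the SAS mean score as abnormal above 0.3 and uses the same by-visit sentence for its shifts.

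SAP 17.6.3 goes further for the AIMS normal/abnormal class: "Shifts from baseline will be summarized by visit, postbaseline overall (based on maximum severity), and treatment group". For AIMS global severity it does not: "These postbaseline changes will be summarized by visit and treatment group".

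Two general rules bear on this. SAP 6.4 says "Unscheduled measurements will not be included in by-visit summaries", and adds: "Unscheduled measurements collected postbaseline will contribute to the derivation of markedly abnormal postbaseline value, and best/worst case value where required (eg, shift tables". SAP 6.3 adds a last-observation row to applicable by-visit tables. That row "is defined as the post-baseline visit at which the last non-missing observation is collected for a subject for a given parameter, including unscheduled visits" or early-termination visits that could not be mapped.

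On treatment during the study, Protocol 10.3.3 says: "Treatment with propranolol (up to 120 mg/day) or amantadine (up to 300 mg/day) will be permitted as needed for akathisia".

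**The concern.** BARS and SAS are named in the protocol's safety objectives and endpoints (5.5, 6.5). Protocol 4.3 presents the enantiomer ratio as a way to limit D2-related side effects, and 7.3.1 reports D2 occupancy of 20-30% after 200 mg and 40-50% after 400 mg. How many subjects at each dose ever developed akathisia or parkinsonism on these scales is therefore a natural safety question.

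A by-visit row gives the prevalence at that visit among subjects rated there. A subject who worsens at Week 1, is treated, and is back to baseline at Week 2 appears in one row only, and no row counts subjects with any worsening. If the worsening was rated only at an unscheduled visit and later ratings exist, it appears in no row. The SAP gives any-time or worst post-baseline summaries for markedly abnormal laboratory values (17.2), QTc categories (17.3), vital signs (17.4), C-SSRS (17.6.2) and the AIMS class (17.6.3). It states no reason for leaving out BARS and SAS.

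**Working it through.** The plan states no figure here, so there is none to reproduce. The check compares the tables and then illustrates the arithmetic.

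**1. Tables side by side**

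| Summary | Classification | By visit | Worst post-baseline |
|---|---|---|---|
| AIMS class (17.6.3) | normal/abnormal | yes | yes |
| AIMS global severity (17.6.3) | worsened/unchanged/improved | yes | no |
| BARS global (17.6.4) | worsened/unchanged/improved | yes | no |
| SAS mean score (17.6.5) | normal/abnormal | yes | no |

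The like-for-like asymmetry is SAS against the AIMS class. The BARS global item is treated the same way as its AIMS counterpart; both lack the row.

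**2. Where each kind of rating goes**

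- Scheduled rating (Weeks 1, 2, 4, 6): its own visit row.
- Early-termination rating: SAP 6.3 Table 1 maps BARS and SAS with contiguous windows (days 1-9, 10-16, 17-30, 31-44), so a rating up to day 44 lands in a visit row.
- Unscheduled rating: no visit row. Section 6.4 allows it into a worst-case value where one is required, but 17.6.4 and 17.6.5 require none. It counts only if it is the last observation.

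**3. Can the ever-worsened count be recovered from the visit rows?** No. With four rows and no unscheduled ratings, it lies between the largest row and the sum of the rows. Rows of 3, 3, 3, 3 fit anything from 3 subjects (the same three at every visit) to 3 + 3 + 3 + 3 = 12 subjects (a different three each time).

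**4. Illustration of the dilution (rates assumed)**

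Let each affected subject be abnormal at k of the 4 visits, with everyone rated at every visit. Averaged over the four rows, a row shows k/4 of the ever-worsened rate:

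- k = 1: 1/4 = 25%
- k = 2: 2/4 = 50%
- k = 3: 3/4 = 75%
- k = 4: 4/4 = 100%, no dilution

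Take 98 per arm (SAP 3.1) and assumed rates of 12% active and 4% placebo. Ever worsened: 98 × 0.12 = 11.8 and 98 × 0.04 = 3.9, about 12 against 4. For one-visit episodes spread evenly, each row shows 12/4 = 3% and 4/4 = 1%, about 3 against 1 subjects.

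Over a range of assumed rates, again with k = 1:

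| Ever worsened, active vs placebo | Difference (points) | Difference per row (÷ 4) |
|---|---|---|
| 8% vs 2% | 6 | 1.5 |
| 12% vs 4% | 8 | 2.0 |
| 16% vs 4% | 12 | 3.0 |
| 20% vs 5% | 15 | 3.75 |

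Even spread makes the largest row as small as it can be. If every one-visit episode fell at Week 1, that row would show all the cases. No test is attached to these shift tables, so the illustration is given in counts and differences only.

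**The case against.** The strongest reply is that EPS is visible elsewhere. Akathisia or parkinsonism reported as an adverse event is tabulated by arm with each subject counted once per preferred term (SAP 17.1), and concomitant medications are tabulated by ATC class and preferred term (SAP 13). This stands. A reader might infer that the plan never reports how many subjects had EPS, or that a dose-related effect could disappear. The documents do not support that; what is missing is the ever-worsened count on the two rating scales. That count still adds something, because adverse events are elicited without specific prompting (Protocol 11.4.1) while the scales are rated systematically.

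A reader might also infer that BARS is treated worse than AIMS throughout. It is not: AIMS global severity is also by visit only.

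Withdrawals are largely covered, by the early-termination mapping and the last-observation row. A reader might further infer that treatment and dropout pull the BARS and SAS mean-change models toward zero. The documents offer nothing to show or size that.

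The loss of unscheduled ratings is of unknown extent. Protocol 7.1 allows unscheduled visits, but nothing schedules BARS or SAS at them. Section 6.4 names shift tables as an example of where worst-case values may be used, and the table templates mentioned in SAP 8 are not in the documents and could include such a row. The text of 17.6.4 and 17.6.5 does not ask for one.

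Finally, Protocol 15.3.6.6 asks only for by-visit descriptives and models and leaves further detail to the SAP. No protocol requirement is breached.

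**Conclusion.** The point holds as a modest safety-reporting gap. As written, 17.6.4 and 17.6.5 do not yield the number of subjects per arm who ever worsened on the BARS global assessment or were ever abnormal on the SAS, and an unscheduled rating that is not the last observation reaches only the listings. The effect is limited to EPS that resolves or is treated while the subject stays on study.

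Its size cannot be fixed from the documents. It ranges from no dilution (EPS present at all four visits) to about one quarter of cases per row (one-visit episodes, evenly spread). This rests on assumed rates and durations and on complete attendance. The statement about withdrawals also assumes that the shift tables count as applicable by-visit tables under SAP 6.3 and so carry the last-observation row. Efficacy inference and Type I error are untouched.

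**What to change.** In SAP 17.6.4 (BARS global assessment) and 17.6.5 (SAS class), replace the by-visit sentence with the form already used in 17.6.3: "Shifts from baseline will be summarized by visit, postbaseline overall (based on maximum severity), and treatment group". State that unscheduled post-baseline ratings count toward the maximum, as 6.4 allows. AIMS global severity could be aligned in the same edit. The cost is one row in two existing tables (three with AIMS global severity), from data already collected.

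Optionally, report by arm the number of subjects who started a medication for a recorded movement-disorder indication after first dose. The ATC and preferred-term table partly covers this, but it does not separate by indication: Protocol 10.3.2 lets beta-blockers continue for stable hypertension, so propranolol use there need not mean akathisia. Indication is recorded (Protocol 10.3), and SAP 13 already gives benzodiazepines, sedatives and hypnotics a count of their own.

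Before a drug list is attached to that count, Protocol 10.3.3 and 10.3.4 must be reconciled. Section 10.3.3 permits propranolol and amantadine for akathisia. Section 10.3.4 prohibits medications for movement disorders other than benztropine, biperiden, trihexyphenidyl and diphenhydramine or agreed equivalents. Which of the two is intended is for the sponsor to settle.

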17.6.5. MODIFIED SIMPSON-ANGUS SCALE (SAS)

Document:

Author:

Version Number:

V2.0

Version Date:

21MAY2020

Template No: CS_TP_BS016 Revision 4
Effective Date: 01Apr2016

Reference: CS_WI_BS005

The Modified SAS is a clinician-rated assessment of neuroleptic-induced Parkinsonism consisting of 10 items. Items are anchor-based, rated on a 5-point scale, and address rigidity, gait (bradykinesia), tremor, glabellar tap, and salivation (Simpson 1970). The SAS mean score is defined as the average of all 10 items and ranges between 0 and 4. Lower values of the SAS mean score indicate milder symptoms. If one or more items are missing at a visit the SAS mean score will be set to missing. SAS is assessed at Visit 2/Baseline, Visit 3/Week 1, Visit 4/Week 2, Visit 5/Week 4, and Visit 6/Week 6.

All summaries and analyses will be based on the SAF population. Descriptive statistics for absolute value and change from baseline in SAS mean score will be displayed at each visit by treatment group. The SAS mean score will be analyzed using MMRM and ANCOVA based on the change from baseline to Week 6 similar to the primary efficacy endpoint, with the baseline SAS mean score value as covariate (see [Sections 16.1.3](#) and [16.1.5.1](#)).

The SAS mean score at each visit will also be classified as 'abnormal' if it exceeds 0.3 ([Rush 2000](#)). Otherwise, non-missing mean scores will be classified as 'normal.' Shifts from baseline will be summarized by visit and treatment group.

17.6.6. PHYSICIAN WITHDRAWAL CHECKLIST (PWC)

The Physician Withdrawal Checklist (PWC) is used to evaluate symptoms of withdrawal after discontinuation of study drug. The scale includes 20 symptoms and each symptom is assessed on a 4 point scale using the following: 0=Not Present, 1=Mild, 2=Moderate and 3=Severe. The score for each question is summed to compute a total score ranging from 0 to 60. If the response to any question is missing, then the total score will be missing.

This checklist will be assessed at the end of treatment visit (Visit 6/Week 6) and Visit 7/Follow-up/Week 7 visit.

All summaries and analyses will be based on the SAF population. The PWC will be summarized using descriptive statistics by visit for the total score. The number and percentage of subjects with a Present response (mild, moderate, or severe) will be provided for each of the 20 PWC items. In addition, responses of mild, moderate and severe will be summarized separately at each visit.

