Subjects who meet eligibility criteria at Screening will return to the study site on Day -1 for confirmation of screening evaluations as well as completion of predose assessments. Eligible subjects (based on confirmation of study entry criteria) will be randomized and dispensed study drug at Day -1.

Per local clinical practice, subjects may be hospitalized for up to 7 days during the first week of treatment with double-blind study drug. Further need for hospitalization will require consultation with the Medical Monitor.

Subjects will self-administer the study drug on an outpatient basis once daily with or without food beginning on Day 1 (the day after the Baseline visit) and continue for 6 weeks (the last dose of study drug will be self-administered by the subject at home on the morning of Visit 6).

Subjects will be instructed to administer study drug as a single oral dose in the morning at approximately the same time each day. Clinic visits are to begin no later than 6 hours postdose, if possible.

During the baseline (Day -1) and treatment period (Days 1 to 42), subjects will have clinic visits at Days -1, 7, 14, and 28. In order to facilitate scheduling of clinic visits, a window of \pm 2 days will be allowed for each clinic visit. Subjects will have a telephone contact at Day 35 (\pm 2).

End of Treatment (EOT)/Early Termination (ET) (Day 42 [\pm 2])

Subjects will have a clinic visit at Day 42 for assessments of efficacy and safety. Subjects who discontinue the study prior to this visit will undergo the procedures and assessments for this visit at the time of discontinuation.

Follow-up Period (Day 49 [\pm 2])

All subjects who received at least one dose of study drug will have a follow-up visit for safety and tolerability assessments 7 (\pm 2) days after their last study drug dose. Assessment of potential withdrawal effects will also be made during the follow-up period.

Efficacy, Safety, and PK/PD Assessments

Efficacy will be evaluated using the MADRS, CGI-BP-S, and HAM-A. Treatment response and symptom remission will be assessed using the MADRS. Additional assessments will include evaluation of functional impairment associated with bipolar depressive symptoms using the SDS total score and symptom severity using the QIDS-SR16 total score.

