11.4.5.6. Physician Withdrawal Checklist

Assessment of potential withdrawal effects will be conducted via the Clinician administered Physician Withdrawal Checklist (PWC) at the End of Treatment visit (Day 42 ± 2 , after completion of efficacy and safety assessments and procedures scheduled for this visit are completed). The PWC will be administered again at the Follow-up visit (Day 49 ± 2).

The PWC is used to evaluate symptoms of withdrawal after discontinuation of study medication. Symptoms are assessed as present or absent and if present then intensity is assessed as mild, moderate, or severe.

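### SAP 17.6.6 summarises the withdrawal checklist visit by visit only, so the planned tables do not show which symptoms are new or worse after study drug is stopped

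*SAP*

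**What the plan says.** Protocol 11.4.5.6 states the purpose of the instrument: "The PWC is used to evaluate symptoms of withdrawal after discontinuation of study medication". SAP 17.6.6 rates 20 symptoms from 0 to 3 ("The score for each question is summed to compute a total score ranging from 0 to 60") and sets two time points: "This checklist will be assessed at the end of treatment visit (Visit 6/Week 6) and Visit 7/Follow-up/Week 7 visit". For completers, Protocol 7.1 puts the end of dosing on the day of the first of these: "the last dose of study drug will be self-administered by the subject at home on the morning of Visit 6". The follow-up visit is 7 (±2) days after the last dose.

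SAP 17.6.6 plans three outputs in the Safety population:

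- Total score: "The PWC will be summarized using descriptive statistics by visit for the total score".
- Items: "The number and percentage of subjects with a Present response (mild, moderate, or severe) will be provided for each of the 20 PWC items".
- Severity: "In addition, responses of mild, moderate and severe will be summarized separately at each visit".

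The section gives no change from Visit 6 to Visit 7, no shift table, and no definition of a new or worsened symptom. SAP 6.3, Table 1, places the PWC in the row that begins "SDS, EQ-5D-5L, Weight, BMI, Waist Circumference, PWC, HbA1C". That row assigns an early-termination (ET) assessment on any of study days 1 to 44 to Visit 6/Week 6.

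**The concern.** A withdrawal checklist is meant to show what appears or gets worse once drug is stopped. The visit schedule supplies what is needed: in completers, one assessment on drug and one off drug in the same person. The planned tables do not link the two. A symptom already present at Visit 6 is counted again at Visit 7, and a symptom that resolves in one subject offsets one that starts in another.

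At stake is the assessment of potential withdrawal effects that Protocol 7.1 says will be made during follow-up. As planned, it would rest on two cross-sectional columns per arm.

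**Working it through.** **1. The plan's own figure.** 20 items × 0 = 0 and 20 items × 3 = 60, so the stated 0 to 60 range is reproduced. The documents give no other figure for the PWC analysis.

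**2. Does another section supply the paired comparison?**

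- SAP 6.2 defines baseline as the last value before first dose. The PWC is first given at Visit 6 (Protocol Table 2), so a change-from-baseline rule has nothing to work on.
- Protocol 15.3.6 contains no PWC analysis.
- SAP 17.6.3 to 17.6.5 give AIMS, BARS and the Modified SAS change scores plus shift or worsened categories. SAP 17.6.6 has no counterpart.
- MADRS and HAM-A stop at Visit 6. Protocol 11.6.4 lists only YMRS, PWC and C-SSRS among the scales at Visit 7.

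So no text in either document pairs the two PWC assessments.

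**3. What the by-visit item percentages can identify.** The item sentence does not itself name the visits. I read it, with the sentences on either side, as a by-visit summary. For one item in one arm, in subjects seen at both visits, let p6 and p7 be the proportions with the symptom present. Let a be the proportion absent at Visit 6 and present at Visit 7 (new onset), and r the proportion present and then absent (resolved). The margins fix only the difference:

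a − r = p7 − p6

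New onset itself is only bounded:

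max(0, p7 − p6) ≤ a ≤ min(1 − p6, p7)

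The documents give no PWC percentages, so the p6 and p7 values below are assumed. The 98 is the planned number randomised per arm in the US and Europe (SAP 3.4), and counts are rounded.

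| p6 | p7 | lower bound for a | upper bound for a | new-onset cases of 98 |
|---|---|---|---|---|
| 30% | 30% | max(0, 0) = 0% | min(70%, 30%) = 30% | 0 to 29 |
| 20% | 30% | max(0, 10%) = 10% | min(80%, 30%) = 30% | 10 to 29 |
| 50% | 40% | max(0, −10%) = 0% | min(50%, 40%) = 40% | 0 to 39 |

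In the first row, an arm where the same 30% keep the symptom and an arm where 30% lose it while a different 30% gain it produce the same table. Severity counts have the same limit: one subject moving from mild to severe and another from severe to mild leave the counts unchanged.

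**4. The total score.** Here less is lost. With the same subjects at both visits, the mean change equals the difference between the two visit means, so it can be read off the planned table. What is missing is the spread of the individual changes and the restriction to the same subjects. SAP 17.6.6 sets a total to missing if any response is missing, so the two visits can have different denominators.

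**5. Which reference value to use.** Protocol 13.1 has early discontinuers undergo the Visit 6 procedures when they discontinue, with no stated maximum gap from the last dose. Together with Table 1, this means that a value labelled Week 6 may have been taken after drug was stopped.

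**The case against.** The strongest reply is that the plan already delivers what was promised. Withdrawal is not among the listed safety objectives or endpoints, and Protocol 7.1 promises only an assessment. Protocol 15.3 calls for summaries by arm, so placebo provides a reference at both visits. It also calls for listings of all CRF data. Adverse events are recorded to the follow-up visit (Protocol 12.3). SAP 17 plans no between-group comparisons for safety data unless specified. The table templates mentioned in SAP 8 are not available here, so a shift table in them cannot be excluded.

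Most of this stands and limits the weight of the point. It does not remove the item-level gap. By-arm columns give net change only, listings are not a summary, and the SAP text specifies no paired output.

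A reader might also infer four stronger things that the documents do not support:

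- **That withdrawal cannot be told apart from residual depression and anxiety.** The 20 items are not listed, so overlap with those symptoms is an assumption. A paired table would not settle it either, since returning illness and withdrawal both appear as worsening after Visit 6.
- **That a withdrawal effect on the total score would be hidden.** If active arms were 3 points below placebo at Visit 6 and level at Visit 7 (assumed values), the planned by-arm table would show −3 and then 0.
- **That the Week 6 column is contaminated.** Off-drug ET values are possible, but the documents show neither their number nor any delay. Mapping an ET value to the only end-of-treatment slot is a natural choice.
- **That a change score is more precise.** With equal SDs, the SE for an arm difference in change, relative to that for Visit 7 totals, is √(2(1 − ρ)), where ρ is the within-subject correlation. This is 1.18 at ρ = 0.3, 1.00 at 0.5 and 0.77 at 0.7. The gain needs ρ above 0.5, and the documents give no value.

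**Conclusion.** The point holds in a limited form. As written, SAP 17.6.6 does not use the paired structure of the PWC, and its item and severity tables do not identify symptoms that are new or worse after stopping drug. With the assumed prevalences above, new onset could lie anywhere in a range 20 to 40 percentage points wide. The limitation is in the planned tables and not in the data, because both assessments are collected.

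The conclusion rests on reading the item summary as by-visit and on the templates adding nothing paired. The priority is low: no primary efficacy endpoint or listed safety endpoint depends on it. Even when corrected, the analysis would show new or worsened symptoms by arm against placebo, without attributing them to withdrawal or to returning illness.

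**What to change.** Add to SAP 17.6.6, by treatment arm and in subjects with both assessments:

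1. For each of the 20 items, the number and percent newly present or worsened from Visit 6/ET to Visit 7.
2. Descriptive statistics for the change in PWC total from Visit 6/ET to Visit 7. A 95% CI versus placebo is optional.

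Flag Visit 6/ET assessments made after study drug had already been stopped, and present the paired summary without them. State the number of subjects with both assessments in each arm.

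The cost is one extra descriptive table from data already collected. No visit, endpoint or alpha allocation changes.
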